5.5 Follow-up of Adverse Events

5.5.1 Follow-up of Non-serious Adverse Events

Non-serious AEs that are identified on the last scheduled contact must be recorded on the AE CRF with the current status noted. All non-serious events that are ongoing at this time will be recorded as ongoing on the CRF. Site personnel will make a follow-up call to the subject 30 days (\pm 3 days) after the last study visit to inquire about any AEs that were ongoing at the time of the last visit and any new AEs and to assess if any new SAEs have occurred.

5.5.2 Follow-up of Serious Adverse Events

SAEs that are **identified on the last scheduled contact** must be recorded on the AE CRF page and reported to the sponsor's designee according to the reporting procedures outlined in [Section 5.3](#). This may include **unresolved previously reported SAEs**, or

Protocol 31-10-270

new SAEs. The investigator should follow these SAEs until the events are resolved, or the subject is lost to follow-up. Resolution means the subject has returned to the baseline state of health, or the investigator does not expect any further improvement or worsening of the subject's condition. The investigator should continue to report any significant follow-up information to the sponsor's designee up to the point the event has been resolved.

This trial requires that withdrawn subjects be actively monitored for SAEs up to 30 days (± 3 days) after discharge from the trial. Any new SAEs reported by the subject to the investigator that occur after the last scheduled contact, and are determined by the investigator to be reasonably associated with the use of the study drug, should be reported to the sponsor's designee. This may include SAEs that are captured on follow-up personal or telephone contact or at any other time point after the defined trial period (ie, up to last scheduled contact). The investigator should follow serious related AEs identified after the last scheduled contact until the events are resolved, or the subject is lost to follow-up. The investigator should continue to report any significant follow-up information to the sponsor's designee up to the point the event has been resolved.

6 Pharmacokinetic or Pharmacodynamic Analysis

No pharmacokinetic or pharmacodynamic assessments will be conducted.

7 Statistical Analysis

The safety and tolerability evaluated will be based on safety parameters, eg, AEs, vital signs, ECGs, laboratory assessments, and injection pain assessments by the subject and investigator. Additionally, the risk of suicide will be evaluated using the C-SSRS. Efficacy will be evaluated using the CGI-S.

Due to the open-label single-arm nature of the study, all data on safety and efficacy/outcome will be summarized using descriptive statistics (eg, mean, standard deviation, maximum, minimum, and proportions).

Withdrawn subjects will not be replaced.

7.1 Dataset for Analysis

Since subjects in this study will be rolling over from another open-label study of aripiprazole IM Depot and will already be exposed to aripiprazole, all enrolled subjects will constitute the core data set for analysis. All safety analyses will be based on this core dataset. The dataset for efficacy outcome analyses will be derived from the core

Protocol 31-10-270

dataset. In particular, for a change from baseline analysis, only subjects having a baseline and a post-baseline value on the efficacy outcome measure will be included.

7.2 Baseline Values

Since subjects will be rolling over in the study from Study 248, evaluations at the Week 52 visit of Study 248 will be used as baseline for this study.

7.3 Primary Outcome Measures

In this safety and tolerability study, the primary measures are (1) frequency and severity of adverse events, (2) frequency and severity of serious adverse events (including adverse events related to laboratory abnormalities), and (3) rates of discontinuation from study due to adverse events.

Safety and tolerability data will be summarized as follows: Incidence of adverse events and serious adverse events (with severity grades) will be tabulated by Medical Dictionary for Regulatory Activities (MedDRA) terms; similarly, incidence of discontinuations due to AE will be tabulated by MedDRA terms.

7.4 Secondary Outcome Measures

Mean change from baseline of vital signs parameters, laboratory tests, and ECG parameters will be provided by visit. Incidence of clinically significant abnormalities in vital signs parameters, laboratory tests, and ECG parameters will be tabulated.

Percentage of subjects showing significant weight gain or loss from enrollment to endpoint (significant weight change is defined as a $\geq 7\%$ increase or decrease in weight) will be provided. Injection site reactions will be summarized by visit using the mean of VAS subject-reported rating scores and investigator's rating of local pain, swelling, redness and induration at the injection site. Data collected on the C-SSRS will be summarized by visit also.

Mean and mean change from baseline in the efficacy endpoint CGI-S score will be summarized by visit. Descriptive statistics of EPS will be provided by calculating mean change from baseline in AIMS, SAS, and BARS. Results will be summarized by visit.

7.5 Sample Size

In this open-label, single arm rollover study, no formal sample computations were employed. The anticipated number of subjects from Study 248 that is predicted to enroll in this study is approximately 500 to 800 subjects.

Protocol 31-10-270

8 Management of Investigational Medicinal Product

8.1 Packaging and Labeling

The study drug will be provided to the investigator(s) by the sponsor or designated agent. The aripiprazole IM Depot formulation will be supplied as aripiprazole 400 mg lyophilized vials packaged in supply cartons labeled similarly to the oral study medication. Prior to injection, vials of aripiprazole IM Depot 400 mg will be reconstituted with a designated quantity of Sterile Water for Injection. A volume corresponding to the dose to be administered (ie, aripiprazole 400 mg or aripiprazole 300 mg) will be withdrawn from the proper vial using an appropriate size syringe.

The reconstituted drug product must be prepared using aseptic technique and administered intramuscularly. The dose must be administered to the subject within the required timeframe of preparation. Needle length for injection of aripiprazole IM Depot will be selected based on BMI (21 gauge, 1.5 inch for BMI \leq 28 kg/m²; 21 gauge, 2 inch for BMI > 28 kg/m²). All doses of aripiprazole IM Depot must be injected into the gluteal muscle, and care must be taken to avoid inadvertent injection into a blood vessel. Specific directions for the reconstitution and administration of IM depot injections will be provided in the Operations Manual.

8.2 Storage

Study drug will be stored in a securely locked cabinet or enclosure. Access should be strictly limited to the investigators and their designees. Neither the investigators nor any designees may provide study drug to any subject not participating in this protocol.

Lyophilized vials of aripiprazole IM Depot should be stored in a refrigerator at 2 to 8°C (36 to 46°F) and protected from light. The clinical site staff will maintain a temperature log in the drug storage area recording the temperature at least once each working day.

8.3 Accountability

The investigator, or designee, must maintain an inventory record of the study drug received, dispensed, administered, and returned to assure regulatory authorities and the sponsor that the study drug will not be dispensed to any person who is not a subject under the terms and conditions set forth in this protocol.

8.4 Returns and Destruction

Upon completion or termination of the trial, all unused and/or partially used study drug must be returned to the sponsor or a designated agent.

Protocol 31-10-270

All study drug returned to the sponsor must be accompanied by the appropriate documentation and be clearly identified by protocol number and trial site number on the outermost shipping container. Returned supplies should be in the original containers (eg, subject kits). The assigned trial monitor should facilitate the return of unused and/or partially used study drug.

If the study drug is authorized to be destroyed at the site by the sponsor, it is the investigator's responsibility to ensure that arrangements have been made for the disposal. Written authorization should be issued by the sponsor, procedures for proper disposal should be established according to applicable regulations, guidelines and procedures, and appropriate records of the disposal should be documented and forwarded to the sponsor.

9 Records Management

9.1 Source Documents

Source documents are defined as the results of original observations and activities of a clinical investigation. Source documents will include, but are not limited to, progress notes, electronic data, screening logs, and recorded data from automated instruments. All source documents pertaining to this trial will be maintained by the investigators and made available for direct inspection by authorized persons as defined in the ICF.

9.2 Data Collection

During each subject's visit to the clinic, a clinician participating in the trial will record progress notes to document all significant observations. At a minimum, these notes will contain:

- Documentation of the informed consent process, including any revised consents;
- The date of the visit and the corresponding Visit or Day in the trial schedule;
- General subject status remarks, including any *significant* medical findings. The severity, frequency, duration, action taken, and outcome of any AEs and the investigator's assessment of relationship to study drug must also be recorded;
- Any changes in concomitant medications or dosages;
- A general reference to the procedures completed;
- The signature (or initials) and date of each clinician (or designee) who made an entry in the progress notes.

In addition, any contact with the subject via telephone or other means that provides significant clinical information will also be documented in the progress notes as described above. Any changes to information in the trial progress notes and other source

Protocol 31-10-270

documents will be initialed and dated on the day the change is made by a site staff member authorized to make the change. Changes will be made by striking a single line through erroneous data (so as not to obliterate the original data), and clearly entering the correct data (eg, ~~wrong data~~ right data). If the reason for the change is not apparent, a brief explanation for the change will be written in the source documentation by the clinician.

Information from the trial progress notes and other source documents will be data entered by investigative site personnel directly onto electronic CRFs in the electronic data capture (EDC) system provided by the sponsor (or sponsor's designee).

9.3 File Management at the Trial Site

It is the responsibility of the investigator to ensure that the trial site file is maintained in accordance with Section 8 of the ICH GCP Guideline and as required by applicable local regulations. The investigator/institution should take measures to prevent accidental or premature destruction of these documents.

9.4 Records Retention at the Trial Site

Regulatory requirements for the archiving of records for this trial necessitate that participating investigators maintain detailed clinical data for the longest of the following three periods:

- A period of at least 3 years following the date on which approval to manufacture the drug is obtained (or, if development of the study drug is discontinued, the date on which development is discontinued); OR
- A period of at least 3 years after the date on which the trial is completed or terminated.
- In addition, longer, region-specific storage requirements may apply as described in the Operations Manual for this trial.

The investigator must not dispose of any records relevant to this trial without either (1) written permission from the sponsor or (2) providing an opportunity for the sponsor to collect such records. The investigator shall take responsibility for maintaining adequate and accurate electronic or hard copy source documents of all observations and data generated during this trial, including the CRF data on the CD-ROM received from the sponsor (or designee). Such documentation is subject to inspection by the sponsor, sponsor's designee, and relevant regulatory authorities. If the investigator withdraws from the trial (eg, relocation, retirement), all trial-related records should be transferred to

Protocol 31-10-270

a mutually agreed-upon designee within a sponsor-specified timeframe. Notice of such transfer will be given to the sponsor in writing, prior to the action taking place.

10 Quality Control and Quality Assurance

10.1 Monitoring

The sponsor has ethical, legal, and scientific obligations to follow this trial carefully in a detailed and orderly manner in accordance with established research principles, the ICH GCP Guideline, and applicable regulatory requirements and local laws. As part of a concerted effort to fulfill these obligations (maintain current personal knowledge of the progress of the trial), the sponsor's monitors (or designees) will visit the site during the trial in addition to maintaining frequent telephone and written communication.

10.2 Auditing

The sponsor's Quality Management Unit (or representative) may conduct audits at the trial site(s). Audits will include, but are not limited to, drug supply, presence of required documents, the informed consent process, and comparison of CRFs with source documents. The investigator agrees to participate with audits conducted at a reasonable time in a reasonable manner.

Regulatory authorities worldwide may inspect the investigator site during or after the trial. The investigator should contact the sponsor immediately if this occurs, and must fully cooperate with the inspections conducted at a reasonable time in a reasonable manner.

11 Ethics and Responsibility

This trial must be conducted in compliance with the protocol, the ICH GCP Guideline, and applicable local laws and regulatory requirements.

12 Confidentiality

All information generated in this trial must be considered highly confidential and must not be disclosed to any persons not directly concerned with the trial without written prior permission from the sponsor. Subject confidentiality requirements of the region(s) where the trial is conducted must be met. However, authorized regulatory officials and sponsor personnel (or their representatives) will be allowed full access to inspect and copy the records. All study drugs, subject bodily fluids, and/or other materials collected shall be used solely in accordance with this protocol, unless otherwise agreed to in writing by the sponsor.

Protocol 31-10-270

Subjects will be identified only by initials and unique subject numbers in CRFs. Their full names may, however, be made known to a regulatory agency or other authorized officials if necessary.

13 Amendment Policy

Appendix 3 Criteria for Identifying Vital Signs of Potential Clinical Relevance

Variable	Criterion Value ^a	Change Relative to Baseline ^a
Heart rate ^b	> 120 bpm < 50 bpm	≥ 15 bpm increase ≥ 15 bpm decrease
Systolic Blood Pressure ^b	> 180 mm Hg < 90 mm Hg	≥ 20 mm Hg increase ≥ 20 mm Hg decrease
Diastolic Blood Pressure ^b	> 105 mm Hg < 50 mm Hg	≥ 15 mmHg increase ≥ 15 mmHg decrease
Orthostatic Hypotension	≥ 20 mmHg decrease in systolic blood and a ≥ 25 bpm increase in heart rate from supine to sitting/standing	Not applicable (baseline status not considered)
Weight	-	≥ 7% increase ≥ 7% decrease

^aIn order to be identified as potentially clinically relevant, an on-treatment value must meet the “Criterion Value” and also represent a change from the subject’s baseline value of at least the magnitude shown in the “Change Relative to Baseline” column.

^bAs defined in “Supplementary Suggestions for Preparing an Integrated Summary of Safety Information in an Original NDA Submission and for Organizing Information in Periodic Safety Updates,” FDA Division of Neuropharmacological Drug Products draft (2/27/87).

Protocol 31-10-270

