3.6.3.3.2 Vital Signs

Vital sign measurements will be performed at baseline, every 6 months (study months are every 4 weeks which is defined as 28 [-2/+10] days), and at Study Completion or the Early Termination visit, and will include body temperature, systolic and diastolic blood pressure, and heart rate. Orthostatic assessments of blood pressure and heart rate will be made after the subject has been supine for at least 5 minutes and again after the subject has been sitting for 2 minutes.

Protocol 31-10-270

A diastolic blood pressure > 105 mm Hg is exclusionary. In addition, subjects should be excluded if they have any other vital sign measurement at screening that, in the investigator's judgment, is medically significant in that it would impact the safety of the subject or the interpretation of the study results. [Appendix 3](#) is included to assist investigators in their assessments of results that may be potentially medically significant, depending on the subject's medical history and clinical presentation.

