4.1 Prohibited Medications

Medications that are prohibited or restricted prior to screening and/or during the trial are listed by phase in [Table 4.1-1](#). No prohibited or restricted medications should be used within the visit windows when transitioning from Study 248 to Study 270. The prohibited and restricted medications also apply to any clinical transition period within allowed visit windows from Study 248 into Study 270.

Protocol 31-10-270

Table 4.1-1 List of Medications Prohibited or Restricted in Study 270	
Psychotropic Medications	
Antipsychotics	Not allowed
Antidepressants (including MAOIs)	Allowed, except for CYP2D6 or CYP3A4 inhibitors or CYP3A4 inducers
Benzodiazepine ^a	Allowed
Mood stabilizers	Allowed
Non-benzodiazepine sleep aids ^a	Allowed
Other Medications	
Anticholinergics	Allowed
Propranolol (for akathisia, tremor, or if taking for cardiac reasons) ^b	Allowed
Varenicline	Not allowed
Nutritional supplements and non-prescription herbal preparations with CNS effects (eg, St. John's Wort, omega-3 fatty acids, kava extracts, GABA supplements, etc.)	Allowed, but use caution
CYP3A4 or CYP2D6 inhibitors or CYP3A4 inducers (see Section 4.2.1)	Not allowed

CNS = central nervous system; GABA = gamma-aminobutyric acid.

Note: No prohibited or restricted medications should be used within the visit windows when transitioning from Study 248 to Study 270. The prohibited and restricted medications also apply to any clinical transition period within allowed visit windows from Study 248 into Study 270.

^aBenzodiazepine use is allowed during the study to manage treatment emergent AEs such as agitation, anxiety, and insomnia; however, non-benzodiazepine sleep aids are recommended for insomnia. Combined use of both drug classes (ie, benzodiazepines and non-benzodiazepine sleep aids) as treatment for insomnia is not allowed. Benzodiazepine use should be discontinued as soon as the AE for which it was initiated subsides, as per the investigator's discretion to avoid any withdrawal effects.

^bSubjects receiving propranolol for heart disease may remain on stable, pre-trial doses, as needed, throughout the study so long as the total dose does not exceed 60 mg/day.

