### **5.5.3 Vital Signs Data**

Vital signs include body temperature, respiration rate, pulse, systolic blood pressure, and diastolic blood pressure in supine and standing position. In addition, body weight and waist circumference are measured. The potential clinically relevant vital sign abnormalities will be listed by subject. Criteria for the potentially clinically relevant vital sign abnormalities are provided in [Appendix 2](#). Incidences of clinical relevant vital signs abnormalities based on the observation from the scheduled and unscheduled post-baseline visits will be tabulated for the safety sample. In addition to waist circumference and weight, vitals sign parameters at each visit, and change from baseline at the post-baseline visits will be summarized for the safety sample. Body weight changes will be evaluated for the safety sample by calculating mean change from baseline and by tabulating the incidence of  $\geq 7\%$  weight gain or loss by visit.

If vital sign assessments are repeated for the same visit, the last repeat values are used for production of summary tables. This is accomplished by sorting patient data by visit date and visit time (if applicable) within the same visit identification.

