### **5.5.6 Other Safety Data Analysis**

#### **5.5.6.1 Special Interested Adverse Events**

Incidence of treatment emergent adverse events of special interest, including EPS-related AEs, weight-related AEs, glucose-related AEs, lipid-related AEs, white blood cell abnormalities, orthostasis, prolactin-related AEs, QT-interval AEs, suicidality-related

AEs, and injection-site-related AEs, will be tabulated for safety sample. In addition, proportion of subjects received anticholinergic medication for treatment-emergent EPS-related events will be assessed for safety sample.

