**Appendix 2 Clinical Relevance Criteria for Vital Sign Abnormalities**

VARIABLE	CRITERION VALUE a	CHANGE RELATIVE TO BASELINE a
HEART RATE b	>120 BPM <50 BPM	INCREASE OF ≥ 15 DECREASE OF ≥ 15
SYSTOLIC BLOOD PRESSURE b	>180 MMHG <90 MMHG	INCREASE OF ≥ 20 DECREASE OF ≥ 20
DIASTOLIC BLOOD PRESSURE b	>105 MMHG <50 MMHG	INCREASE OF ≥ 15 DECREASE OF ≥ 15
ORTHOSTATIC HYPOTENSION	≥ 20 MMHG DECREASE IN SYSTOLIC BLOOD PRESSURE AND ≥ 25 BPM INCREASE IN HEART RATE FROM SUPINE TO SITTING/STANDING	
WEIGHT	-	INCREASE ≥ 7% DECEASE ≥ 7%
TEMPRATURE	≥37.8°C	INCREASE ≥1.1°C

a In order to be identified as “clinically relevantly abnormal,” an on-drug value must meet the “Criterion Value” and also represent a change from the patient’s pretreatment value of at least the magnitude shown in the “Change Relative to Baseline column.

b As defined in “supplementary suggestions for Preparing an integrated Summary of Safety Information in an Original NDA Submission and for Organizing Information in period safety Updates,” FDA Division of Neuropharmacological Drug Products draft (2/27/87)

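### The orthostatic hypotension row counts a postural systolic fall only when heart rate also rises by at least 25 bpm, so the vital-sign incidence table understates postural falls by an amount the documents cannot fix

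*Protocol*

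**What the plan says.** Protocol Appendix 3 defines the row as "≥ 20 mmHg decrease in systolic blood and a ≥ 25 bpm increase in heart rate from supine to sitting/standing". SAP Appendix 2 has the same rule: "≥ 20 MMHG DECREASE IN SYSTOLIC BLOOD PRESSURE AND ≥ 25 BPM INCREASE IN HEART RATE FROM SUPINE TO SITTING/STANDING". The protocol states that baseline status plays no part in this row. The heart rate, systolic and diastolic rows carry footnote b, which cites an FDA draft. The orthostatic row does not carry it, and neither document explains the 25 bpm condition.

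Paired readings are planned. Protocol 3.6.3.3.2 calls for orthostatic blood pressure and heart rate "after the subject has been supine for at least 5 minutes and again after the subject has been sitting for 2 minutes". SAP 5.5.3 instead describes "diastolic blood pressure in supine and standing position", and the criterion itself names both upright postures.

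SAP 5.5.3 tabulates the incidence of vital-sign abnormalities in the safety sample over all visits after baseline, planned or not (CT-14.1), and lists them by subject (CT-11.1). SAP 5.5.6.1 also makes orthostasis a topic of special interest among adverse events: "orthostasis, prolactin-related AEs, QT-interval AEs". Protocol Table 4.1-1 allows propranolol for akathisia, tremor or cardiac reasons.

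**The concern.** The row's name promises a count of postural pressure falls. Its rule counts only those falls accompanied by a large heart-rate rise. A reader of CT-14.1 would take a low figure to mean that few subjects had such falls, when it could equally mean that few had both components at one assessment.

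Collecting long-term safety data is the trial's secondary objective, the SAP singles out orthostasis, and Protocol 1.1 notes affinity for alpha1-adrenergic receptors. Sites take supine and upright readings for this purpose, and this row is the only planned analysis that pairs them. Propranolol is a beta-blocker and would be expected to blunt the heart-rate rise, so misses should be more frequent among its users. The documents do not say how many subjects take it.

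**Working it through.** **1. Can another row catch a missed fall?** Take supine 150 mmHg and 70 bpm, upright 110 mmHg and 94 bpm, with diastolic pressure between 50 and 105 mmHg throughout.

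| CT-14.1 row | Rule | Result |
|---|---|---|
| Orthostatic hypotension | systolic fall ≥ 20 and heart-rate rise ≥ 25 | 40 and 24: not met |
| Systolic pressure | > 180 or < 90, plus change from baseline | not met |
| Heart rate | > 120 or < 50, plus change from baseline | not met |
| Diastolic pressure | > 105 or < 50, plus change from baseline | not met |

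The weight and temperature rows do not bear on posture. A 40 mmHg postural fall therefore appears nowhere in the table.

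**2. How large is the undercount?** The plan states no expected incidence, so there is no figure to reproduce, and it gives no postural distributions. The following are assumptions:
- systolic fall: mean 2 to 5 mmHg, SD 9 to 12;
- heart-rate rise: mean 4 to 8 bpm, SD 7 to 9;
- correlation between fall and rise: 0 to 0.5, bivariate normal.

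Let p = P(fall ≥ 20) = 1 − Φ((20 − mean)/SD), and let j = P(fall ≥ 20 and rise ≥ 25). The share of falls counted is q = j/p, and the ratio of the two rates is p/j.

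| Fall mean/SD | Rise mean/SD | Correlation | p | j | p/j |
|---|---|---|---|---|---|
| 2/9 | 4/7 | 0 | 2.28% | 0.003% | 741 |
| 5/12 | 4/7 | 0 | 10.56% | 0.014% | 741 |
| 2/9 | 8/9 | 0.5 | 2.28% | 0.48% | 4.7 |
| 5/12 | 8/9 | 0.5 | 10.56% | 1.32% | 8.0 |

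With zero correlation the ratio is 1/P(rise ≥ 25). For the first row, (25 − 4)/7 = 3, 1 − Φ(3) = 0.00135, and 1/0.00135 = 741. Over a grid on these limits p runs from 2.28% to 10.56%, j from 0.003% to 1.32%, and p/j from 4.7 to 741. At one assessment of 500 to 800 subjects, the systolic fall alone gives about 11 (500 × 2.28%) to 84 (800 × 10.56%) subjects. The combined rule gives fewer than 1 to about 11 (800 × 1.32%).

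**3. What happens over visits?** The tabulated incidence accumulates. Protocol 3.6.1.4 lists 17 six-monthly visits, and SAP Figure 3-1 shows vital signs every 3 months before Amendment 4. Assuming independent visits and full follow-up, which push the figures up, cumulative incidence over k visits is 1 − (1 − rate)^k.

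| Setting | Visits | Systolic fall alone | Combined rule |
|---|---|---|---|
| p = 2.28%, j = 0.003% | 17 | 32.4% | 0.05% |
| p = 3%, q = 0.10, so j = 0.30% | 4 | 11.5% | 1.2% |
| p = 3%, q = 0.10, so j = 0.30% | 17 | 40.4% | 5.0% |
| p = 10.56%, j = 1.32% | 17 | 85.0% | 20.2% |

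**4. Wider assumptions.** Take fall mean/SD of 0/10, 3/10 and 5/12; rise mean/SD of 5/7, 8/8, 10/10 and 15/10; and correlation 0, 0.3 and 0.6. In these 36 scenarios q runs from 0.002 to 0.70 and is below one half in 33. The combined rate is below 1% per visit in 25, but below 1% over 17 visits in only 6.

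**The case against.** The strongest reply is that protocol and SAP agree on a prespecified rule, and preferring another threshold is a matter of taste. That stands against replacing the rule, but not against showing its components beside it.

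A reader might infer that the incidence will be close to zero by construction. The documents do not support this. Requiring two conditions gives a subset, not an almost empty set, and incidence accumulates over visits. A reader might also state as fact that most large falls go uncounted. That needs the share of falls with a 25 bpm rise, which neither document gives. It holds throughout the ranges in step 2 and in 33 of the 36 wider scenarios, but remains an assumption.

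Other routes exist. Orthostasis adverse events are tabulated without this rule (CT-8.2.12). However, Protocol 5.2 elicits events with an open question about how the subject has felt, so that table depends largely on reported symptoms. CT-14.3 summarises vital signs by visit, and the difference between positional means gives the mean postural change in subjects with both readings. It does not give the number of subjects with a large fall. PDATA-11 lists the readings but does not count falls.

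One objection stands in full. The trial has one arm, subjects enter already treated, baseline is on drug, and this row ignores baseline. A systolic-only count would not show whether the drug lowers upright pressure.

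**Conclusion.** The point holds in a limited form. The row can only undercount postural systolic falls, no other row of CT-14.1 is designed to count them, and no reason is given for the heart-rate condition. Under the normal model and the ranges assumed in step 2, the combined rule is met about 5 to 740 times less often per assessment than the systolic fall alone. That spread is too wide to serve as an estimate, and the documents cannot narrow it. The propranolol effect is an expectation about direction, not size.

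The posture conflict is firmer because it rests on text alone: sitting in Protocol 3.6.3.3.2, standing in SAP 5.5.3, and either in the two appendices. The passages must be reconciled, since posture determines what the row measures.

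This is a cheap improvement to a descriptive safety table. It does not threaten the trial's conclusions.

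**What to change.** Change the SAP only, in Appendix 2 and tables CT-11.1 and CT-14.1:
- Keep the prespecified row and label it as the combined criterion.
- Add a row for a supine-to-upright systolic fall of at least 20 mmHg alone.
- Add a row for a supine-to-upright heart-rate rise of at least 25 bpm alone.
- In the same edit, reconcile the upright posture across Protocol 3.6.3.3.2, SAP 5.5.3 and the two appendices, and use the reconciled wording in all three rows.

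The SAP already supplements protocol criteria in this way: section 5.5.2 adds potassium and neutrophil cut-offs, and Appendix 2 adds a temperature row. Leave Protocol Appendix 3 as it is, because it also guides investigators' eligibility judgements.

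The cost is two rows from data already collected. The downside is a higher reported count of postural falls, so a table note should say that the counts are descriptive and do not show a drug effect.
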